### Pharmacokinetics

Isoniazid is generally well absorbed; food and antacids decrease the rate, but not the extent of absorption. The peak blood levels of isoniazid, 3 to 5  $\mu\text{g}/\text{ml}$ , are obtained 30 minutes to 2 hours after ingestion of routine doses. It diffuses into all body fluids and cells and penetrates into the caseous material of a tuberculoma or pulmonary cavity. In the liver, it is acetylated to inactive metabolites, and 75% to 95% of the dose is excreted as inactive metabolites in the urine within 24 hours. Isoniazid clearance rates depend on 2 metabolic phenotypes, slow and fast acetylation. The isoniazid AUC among persons who have fast acetylation is 30% to 50% of that among persons who have slow acetylation. Because isoniazid is well tolerated over a wide range of therapeutic doses, a single dose per body mass is recommended. Persons who have rapid acetylation achieve effective concentrations, while persons who have slow acetylation do not experience increased toxicity. Half-life ( $t_{1/2}$ ) may vary from 1 hour in fast acetylators ( $t_{1/2} < 90\text{min}$ ) to 3 hours in slow acetylators ( $t_{1/2} > 90\text{min}$ ).

### Drug-drug interactions

Isoniazid decreases the clearance of some medications that are metabolized in the liver (particularly carbamazepine, phenytoin, diazepam).

### Toxicity

The total incidence of all adverse effects from isoniazid is approximately 5%, many of which do not require discontinuation of the drug. Peripheral neurotoxicity is dose dependent and it is uncommon (<0.2%) at conventional doses. The risk of peripheral neuritis increases for persons who are malnourished or predisposed to neuritis by other illnesses. Concomitant administration of pyridoxine (vitamin B6) is recommended for HIV positive person in South Africa. It will be given to every participant in this trial. Other nervous system reactions are rare at normal doses, and they include convulsions, encephalopathy, optic neuritis, memory impairment, and psychosis. Gastrointestinal adverse effects include nausea, vomiting, and epigastric distress. Asymptomatic elevation of aminotransferases is common and occurs in 10-20% of persons receiving isoniazid. However, idiosyncratic severe hepatic reactions are uncommon but are more likely in older persons (up to 2.3% hepatitis incidence in persons more than 50 years old), and

may be life threatening. Daily consumption of alcohol increases the risk of isoniazid-associated hepatotoxicity by approximately 4-fold. The risk of isoniazid-induced hepatotoxicity may also be increased in the postpartum period. The prodromal symptoms of hepatotoxicity are anorexia, nausea, vomiting, fatigue, malaise, and weakness; persons who take isoniazid and have these symptoms should stop therapy and be evaluated immediately.

### Dosage

According to South African guidelines the recommended dose of isoniazid for the treatment of TB is 300 mg.

### ***Pyrazinamide***

Pyrazinamide is an analog of nicotinamide and has unique activity against *M. tuberculosis*, allowing the duration of treatment to be decreased from 9 months to 6 months (assuming rifampin is used throughout). The mechanism of action of pyrazinamide remains unknown.

### Pharmacokinetics

Pyrazinamide is well-absorbed from the gastrointestinal tract and widely distributed into all tissues. Usual doses are 15-30 mg/kg/d, up to 2 gm/d. Peak serum concentrations of about 45 µg/ml are achieved approximately 2-3 hours after a dose. Food and antacids do not significantly affect the absorption of pyrazinamide. The half-life of pyrazinamide is approximately 9-10 hours, and is prolonged in the presence of hepatic insufficiency. Pyrazinamide is metabolized to pyrazinoic acid by the hepatic microsomal enzyme pyrazinamide deamidase. Approximately 40% of a dose is recovered in the urine as pyrazinoic acid and an additional 4% is excreted in the urine as the unchanged parent drug. The remaining drug is thought to be excreted in the bile.

### Drug-drug interactions

There are no known clinically significant drug-drug interactions involving pyrazinamide.

### Toxicity

The most frequent side effects are skin rash, gastrointestinal intolerance, hepatotoxicity (1.3%), arthralgias (1-7%), hyperuricemia due to blockade of urate excretion (up to 66%), and rarely acute gouty arthritis. These side effects are seldom dose-limiting. Asymptomatic elevations in serum uric acid are frequent, usually occur during the first or second month of treatment, and are self-limited and require no specific treatment. Minor arthralgias also may occur during pyrazinamide treatment and can usually be treated with salicylates or non-steroidal inflammatory agents such as indomethacin while continuing the drug. The most common serious side effect of pyrazinamide is hepatotoxicity.

### Dosage

According to South African guidelines the recommended dose of pyrazinamide for the treatment of TB is 20-25 mg/kg.

### ***Ethambutol***

Ethambutol is an ethylene derivative of butane that interferes with cell wall synthesis in mycobacteria; other bacteria are uniformly resistant to ethambutol. In the treatment of human TB, ethambutol is effective in preventing the emergence of drug resistant strains, although it has no sterilizing activity at clinically-tolerated doses.

### Pharmacokinetics

Ethambutol is well absorbed from the gastrointestinal tract, reaching peak serum concentrations of 3-5 mcg/ml in normal volunteers 2-4 hours after a dose. Food slows absorption and decreases the peak serum concentration by 10-20%, but has no effect on the total systemic exposure (AUC). Antacids decrease both the peak serum concentration and AUC, and so should not be administered at the same time. Ethambutol is primarily eliminated by the kidneys as unchanged drug; the serum half-life averages 4 hours. Patients with renal insufficiency are prone to accumulation of the drug and the resultant toxicity.

### Drug-drug interactions

There are no known drug-drug interactions involving ethambutol.

### Toxicity

Ethambutol is usually well-tolerated with low rates of skin rash, nausea, vomiting, or diarrhea. Fever, allergic reactions, abdominal pain, mental status changes, peripheral neuropathy, and increased liver function tests have rarely been associated with ethambutol. Adverse events occur in less than 2% of patients receiving ethambutol at the 15 mg/kg dose and include decreased visual acuity (0.8%), rash (0.5%) and asymptomatic hyperuricemia. The most common serious side effect of ethambutol is retinal toxicity, often first perceived as a decrease in color perception. Patients receiving ethambutol should be instructed about symptoms of ocular toxicity. If stopped promptly, permanent visual loss is rare among patients with ethambutol-related retinal toxicity. Rates of retinal toxicity are very low when the drug is given for relatively short periods, as is the case in this study.

### Dosage

According to South African guidelines the recommended dose of ethambutol for the treatment of TB is 15-20 mg/kg. This is the dosage that will be used for this study.

### ***Pharmacy: Product Supply, Distribution, and Accountability***

Pravastatin, Rifafour, and vitamin B6 will be supplied through the study. An FDA-approved preparation of Pravastatin 40 mg tablets will be made available through the National Institute of Allergy and Infectious Diseases (NIAID) Clinical Research Products Management Center (CRPMC). The site pharmacist can obtain the study product for this protocol by following the instructions in the manual Pharmacy Guidelines and Instructions for DAIDS Clinical Trials Networks in the section Study Product Management Responsibilities. Rifafour and vitamin B6 will be obtained in South Africa; Rifafour will be obtained from the National TB Program (purchased from Sanofi-Aventis) and B6 from a commercial distributor. Rifafour will be given in doses consistent with South African guidelines.

Rifafour dosage by pre-treatment body weight

Rifafour = Rifampin/isoniazid/pyrazinamide/ethambutol (150 mg/75 mg/400 mg/275mg)

30-37 kg 2 tabs

38-54 kg 3 tabs

55-70 kg 4 tabs

>70 kg 5 tabs

#### Study Product Accountability

The site pharmacist is required to maintain complete records of all study products received from the NIAID CRPMC and subsequently dispensed. All unused study products must be returned to the NIAID CRPMC (or as otherwise directed) after the study is completed or terminated. The procedures to be followed are provided in the manual Pharmacy Guidelines and Instructions for DAIDS Clinical Trials Networks in the section Study Product Management Responsibilities.

#### **14. The rationale for choice of statin and dose**

Pravastatin was selected for testing in this safety/PK study based on its favorable CC50/EC50 values and demonstration of adjunctive activity against chronic TB in the standard mouse model. Specifically, pravastatin demonstrated the least toxicity of all statins in our assays (CC50 > 1.25 mM and > 10 mM in THP-1 and Vero cells, respectively) and was one of 3 statins for which an EC50 could be obtained within the tested range in THP-1 cells (7.8  $\mu$ M), yielding a highly favorable CC50/EC50 > 160.3. Importantly, pravastatin showed dose-dependent activity against chronic TB in the mouse model, and improved the percent surface area of lung involved by inflammation. Adjunctive therapy with pravastatin 50 mg/kg, which yields human-like drug exposures following an 80-mg dose, significantly reduced the lung bacillary burden in a clinically relevant mouse model of necrotic TB granulomas (C3Heb/FeJ mice) relative to controls receiving the first-line regimen alone. Although simvastatin also showed a highly favorable CC50/EC50 ratio in macrophages and adjunctive activity in the two different mouse models of chronic TB, several factors dampened our enthusiasm for this agent relative to pravastatin. Based on our PK data, simvastatin is almost entirely converted to its acid metabolite in mice, whereas in humans metabolism to simvastatin acid is ~1:1. Since we do not know if the parent drug or acid metabolite is responsible for the anti-TB effect, it is possible that the mouse data overestimate the adjunctive action of simvastatin. Perhaps more importantly, peak concentrations of both simvastatin and simvastatin acid are greatly reduced (by 90%) by rifampin (69). On the other hand, pravastatin exposures are reduced by only 30-50% during co-administration with rifampin. Our PK data suggest that drug clearance and exposures differ markedly between mice and humans. Given that we observed a dose-responsive anti-TB effect with pravastatin adjunctive therapy in mice and the known drug interactions between pravastatin and rifampin in humans, we will study the highest clinically recommended dose of pravastatin in this clinical trial. The anti-TB effect of adjunctive statin therapy observed in mice was accompanied by a reduction in serum IL-6 ([Figure 9](#)) to levels seen in uninfected mice. In addition to IL-6, a recent thesis project at JHU investigating predictors of respiratory impairment in TB identified levels of the cytokines IL-1 $\beta$  and TGF- $\beta$  as being directly proportionate and levels of the cytokines IL-12 and TIMP-2 as being inversely proportionate to changes in St. George's respiratory questionnaire scores during TB treatment ([name], unpublished).

#### **15. Justification and safety information if FDA-approved drugs will be administered for non-FDA approved indications or if doses or routes of administration or participant populations are changed.**

The goal of this study is to evaluate pravastatin as host-directed therapy for TB, a non-approved indication. Pravastatin has favorable, dose-dependent activity against chronic TB in two different mouse models. Pravastatin exposures are reduced by 30-50% during co-administration with rifampin (70). Therefore, we anticipate that a dose of pravastatin 160 mg daily when co-administered with rifampin will give similar pravastatin exposures as monotherapy with pravastatin 80 mg daily. However, to address safety concerns regarding the unknown effect of co-administering pravastatin with the other anti-TB drugs (isoniazid, ethambutol, and pyrazinamide) and to minimize study risk to participants, we will initially recruit a cohort

of 5 participants to assess safety/tolerability of pravastatin 40 mg daily in combination with standard of care (Rifafour) prior to further study drug dose escalation. If this dose is well tolerated when given with Rifafour, we will recruit 10 participants to receive pravastatin 80 mg daily and Rifafour. If it is determined that this dose, when co-administered with Rifafour is well-tolerated, yet the mean pravastatin exposures during adjunctive therapy are reduced by  $\geq 40\%$  relative to pravastatin monotherapy in the same patients (as assessed prior to initiating anti-TB drugs), we will increase the dose of pravastatin incrementally up to a maximum of 160 mg/d, in order to achieve drug exposures equivalent to those of pravastatin 80 mg/d given as monotherapy.

**16. Justification and safety information if non-FDA approved drugs without an IND will be administered.**

Not applicable

**17. Study statistics**

***Primary outcome variable.***

Safety and tolerability of pravastatin adjunctive therapy relative to standard treatment

***Secondary outcome variables***

Steady-state PK of pravastatin among patients with pulmonary TB receiving co-administered Rifafour (isoniazid, rifampin, pyrazinamide and ethambutol)

**18. Statistical Analysis Plan**

***Hypothesis***

Pravastatin given at the standard clinically recommended dose will be safe and well tolerated, and pravastatin drug exposures will not be significantly altered following co-administration with rifampin in the 14-day study.

***Sample size***

The sample size will be between 5 and 35 evaluable participants, who will be recruited into the following arms: 1) Standard-of-care regimen (Rifafour) + pravastatin 40 mg daily (5 evaluable participants); 2) Standard-of-care regimen (Rifafour) + pravastatin 80 mg daily (10 evaluable participants); 3) Standard-of-care regimen (Rifafour) + pravastatin 120 mg daily (10 evaluable participants); 3) Standard-of-care regimen (Rifafour) + pravastatin 160 mg daily (10 evaluable participants). Participants in Arms 2, 3, and 4 (10 participants each) will only be recruited if necessary, i.e., if pravastatin 40 mg is well tolerated and safe, and if escalated doses are also tolerated and safe, yet drug exposures are reduced by  $\geq 40\%$  in participants due to the known interaction with rifampin.

A sample size of 10 evaluable participants for pravastatin PK analysis was chosen based on within-subject variability (CV%) of statin AUC in interaction studies ranging from 6-60% and a within-subject coefficient of variation (CVw) of 33%. With 10 evaluable participants per arm, the precision (i.e., half width of the 90% confidence interval on the log scale) for the treatment difference will be within 26% of the point estimate for AUC. If the point estimate of the ratio of geometric mean is 1, then 90% confidence interval will be approximately (0.74, 1.35).

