The elimination rate constant ( $k_e$ ) will be determined by a linear regression analysis using the last 3–8 points on the plot of the natural logarithm of the plasma concentration-time curve. The  $t_{1/2}$  value will be calculated from the equation  $t_{1/2} = \ln 2/k_e$ . AUC values will be calculated by the linear trapezoidal rule for the rising phase and the log-linear trapezoidal rule for the descending phase, with extrapolation to infinity, when appropriate, by dividing the last measured concentration by  $k_e$ . Results will be expressed as mean values ( $\pm$  s.d.). 95% confidence intervals will be calculated for the mean differences between the baseline pravastatin and rifampin co-administration phases for  $AUC(0-\infty)$ ,  $C_{max}$  and  $t_{1/2}$ . Statistical comparisons of the pharmacokinetic variables (except  $t_{max}$ ) will be carried out by the Student t-test for paired values (two-tailed), and the Wilcoxon signed-rank test will be used for analysis of  $t_{max}$ . Logarithmic transformation of  $C_{max}$  and AUC values will be done prior to statistical analysis. The effect of rifampin (and other anti-TB drugs) on the  $AUC(0-\infty)$  of pravastatin will be assessed with a t-test of log-transformed values. The analysis will be performed with Systat for Windows, V6.0.1 (SPSS Inc., Chicago, Ill). Statistical significance will be taken as  $P < 0.05$ .

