#### ***Decision-making algorithm for initiating new dosing cohorts***

The study will be monitored by a DSMB, which will review the safety data for each cohort and will give approval before initiation of each possible dose escalation. Specifically, study drug dose will not be escalated and the study if any three participants develop grade 3 or higher musculoskeletal/CK-related adverse events (AEs), LFT-related AEs ( $> 5 \times UNL$  without symptoms, but  $> 3 \times UNL$  with symptoms or bilirubin  $> 2 \times ULN$ ) or any type of grade 4 event regardless of causal attribution. Study drug dosage will be escalated only if the dose is deemed safe/tolerable based on the above rules and the mean pravastatin AUC is reduced by  $\geq 40\%$  relative to the pre-Rifafour value. Study participants in whom the study drug has been discontinued will remain in the study until the final clinical visit and laboratory evaluation. In the event of study product discontinuation, management of the standard-of-care TB drugs will revert to the site clinician as per national guidelines.

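### The sample-size precision statement is inconsistent: a 26% log-scale half-width gives a 90% interval of about (0.77, 1.30), not (0.74, 1.35), and the analysis plans only 95% intervals

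*Combined protocol and SAP*

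**What the plan says.** Section 18, Sample size, bases the number of participants for the PK analysis on the precision of a within-subject comparison. The variability input is statin AUC data "ranging from 6-60% and a within-subject coefficient of variation (CVw) of 33" per cent. For 10 evaluable participants per arm the precision is given as the "half width of the 90% confidence interval on the log scale) for the treatment difference will be within 26" per cent of the point estimate for AUC. The next sentence turns this into an interval: "If the point estimate of the ratio of geometric mean is 1, then 90% confidence interval will be approximately (0.74, 1.35".

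Section 18, Data Analysis, describes the comparison itself. Each participant's baseline exposure to pravastatin alone is compared with exposure after 14 days with the TB regimen. The comparison "will be carried out by the Student t-test for paired values (two-tailed"), on log-transformed AUC and Cmax, with significance at P < 0.05. On intervals it says that "95% confidence intervals will be calculated for the mean differences between the baseline pravastatin and rifampin co-administration phases for" AUC(0–∞), Cmax and half-life. No 90% interval appears there.

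Under the decision-making algorithm for new dosing cohorts, the dose goes up only if it is judged safe "based on the above rules and the mean pravastatin AUC is reduced by" 40% or more against the pre-Rifafour value.

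**The concern.** The half-width and the interval are presented as the same precision, at the same confidence level and for the same n. Once a half-width is defined on the log scale, the interval at a ratio of 1 follows from it directly, whatever CV or degrees of freedom lie behind it. The printed limits do not follow.

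This passage is the only quantitative justification for 10 participants per arm, and Data Analysis names pravastatin exposure as a primary endpoint alongside safety. The text does not show which confidence level or degrees of freedom produced the printed limits. The level used for sizing (90%) also differs from the level planned for the report (95%), so neither sizing figure tells the reader how wide the reported interval should be.

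**Working it through.** **Inputs.** From Sample size: n = 10 per arm, within-subject CV 33%, 90% two-sided interval, log scale, stated half-width 26%, stated interval (0.74, 1.35). From Data Analysis: paired t-test, hence 9 df with n = 10; log transformation of AUC; 95% intervals.

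**Step 1: the two stated figures compared, with no other assumption.**
- Half-width 0.26: exp(−0.26) = 0.771 and exp(0.26) = 1.297, so (0.77, 1.30).
- Interval (0.74, 1.35): −ln 0.74 = 0.301 and ln 1.35 = 0.300, so a half-width of about 0.30.

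The printed interval is symmetric on the log scale (0.74 × 1.35 = 0.999), so the two half-widths are directly comparable.

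**Step 2: reproduce the plan's half-width from its inputs.**
- Log-scale within-subject SD: σ = √ln(1 + 0.33²) = 0.3215.
- Standard error of the paired difference: σ × √(2/10) = 0.1438.
- 90% half-width: t(0.95, 9 df) × SE = 1.833 × 0.1438 = 0.2636.
- Interval at a ratio of 1: (0.768, 1.302).

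The 26% is reproduced; the interval is not. On the log scale the stated interval is 0.3005/0.2636 = 1.14 times as wide.

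**Step 3: could another 90% calculation give (0.74, 1.35)?** The log SD was taken as 0.3215 or as 0.33, and the quantile as t on 8, 9 or 18 df or the normal value, all with standard error σ√(2/n). The half-widths run from 0.237 to 0.274, and the widest interval is (0.76, 1.32). A 90% half-width of 0.30 on the paired analysis would need a CV of about 38% at n = 10, or n of about 8 at CV 33% (half-width 0.305).

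**Step 4: possible origins of the printed limits.**
- 26% applied on the ratio scale and inverted: 1 − 0.26 = 0.74 and 1/0.74 = 1.351.
- A 95% interval on 18 df: t(0.975, 18 df) = 2.101, half-width 0.302, interval (0.739, 1.353).

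The first departs from the stated log scale. The second departs from the stated 90% and from the paired design. The document does not say which, if either, was used.

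**Step 5: the 95% interval on the same inputs.** t(0.975, 9 df) = 2.262; half-width 2.262 × 0.1438 = 0.325; interval (0.72, 1.38). That is 0.3253/0.2636 = 1.23 times the 90% width.

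**The case against.** The best defence is that the 26% was meant on the ratio scale, as a distance from the point estimate. The lower limit is then 0.74 and its reciprocal 1.35, exactly as printed, and the fault is a label rather than a calculation. This may well be how the figure arose, but it does not rescue the text. The half-width is expressly defined on the log scale, 1.35 is 35% above 1 and so not within 26% of it, and this reading does not follow from a CV of 33% with 10 participants.

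The second argument is that the slip is harmless. The recomputed interval lies inside the stated one, so the plan promises less precision than it would deliver at the assumed CV. That is correct, and it is why the point is minor.

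Third, sizing on a 90% interval and reporting 95% intervals is not in itself an error, and nothing in Sample size says the 90% interval is the one to be reported. This also stands: that part is a request for alignment, not a correction. Moreover, Data Analysis speaks of mean differences and does not say that the log-scale interval will be back-transformed to a ratio. The figure (0.72, 1.38) therefore assumes that it will be.

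Finally, because the origin of the printed limits is unknown, the sponsor may find that the label rather than the number needs changing. The fix allows for this.

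**Conclusion.** The concern holds. On the plan's own definition, the half-width of 26% and the interval (0.74, 1.35) cannot both be right. The 26% follows from the stated CV, sample size and paired analysis, so the interval is the more likely error: at 90% it should read about (0.77, 1.30), a log half-width of 0.264 against the 0.30 implied by the printed limits.

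The mismatch itself needs no assumption. The recomputed interval rests on CV 33%, 10 evaluable participants and 9 df. The 95% interval of (0.72, 1.38) rests in addition on back-transformation to a ratio; on the log scale it is 23% wider than the 90% interval used for sizing.

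Severity is minor. The stated 90% interval is too wide rather than too narrow, the choice of 10 per arm is unaffected, and escalation compares the mean AUC reduction with 40% as a point estimate, so no interval enters that decision.

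**What to change.** In Section 18, Sample size, restate the 90% interval at a ratio of 1 as about (0.77, 1.30) and state that it rests on 9 df for the paired analysis. If the sponsor's records show that the printed limits came from a different confidence level or different degrees of freedom, correct those labels and the half-width together so that all four items agree.

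Then use one confidence level in Sample size and Data Analysis. Either add the 90% interval for the geometric mean ratio to Data Analysis, or restate the sizing at 95% as a half-width of 0.33 and an interval of (0.72, 1.38). In either case, say that the log-scale interval will be back-transformed to a ratio.

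Optionally, show the precision at the escalation threshold as well: at a ratio of 0.60 (a 40% reduction), the 90% interval is 0.60 × (0.768, 1.302) = (0.46, 0.78).

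The cost is a change of SAP wording. Sample size, data collection and the escalation rule stay as they are.
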